#### *Aim 1 Competitive Work Outcome Measures: Collected Monthly*

The competitive work outcomes are gold standard in VA work studies. In Aim 1, the primary outcome is total weeks worked in competitive jobs. The secondary work outcome is steady competitive work status, defined as working at least 50% of the study period (at least 19.5 weeks out of 38 weeks). Also standard procedure in work studies and used in CBTw pilots, work outcomes will be collected monthly by onsite RAs via Veteran self-report monthly work update form (Appendix 8), and verified with CAPRI/CPRS/JLV SE notes (i.e. SE staff notes will be reviewed for data regarding hours and weeks worked) and directly with SE staff using a data collection form (Appendix 9), as needed. Additional verification layers will be used under any of the following conditions: monthly work update forms are not fully completed; conflicting or unclear information is reported (e.g., Veteran reported only working two days during a month when s/he is employed full time); Veterans report having difficulty recalling their work during the past month. Work outcomes may be collected in person or by phone.

#### *Aim 2 Health and Recovery Outcomes: Collected at baseline, posttreatment, 6 & 9 months*

Used in the CBTw pilot studies and across the SMI literature, subjective recovery pertinent to work will be measured using the Recovery Assessment Scale (RAS), a 41 item, self-report measure with higher scores indicating stronger recovery attitudes (scored on a 1 to 4 Likert scale); the RAS was developed and validated in people with SMI.

Psychiatric symptoms will be assessed using the adult version DSM-5 Level 1 Cross-Cutting Symptom Measure (CCSM), a 23-item, Likert response (scored on a 0 to 4 scale), self-rated instrument that assesses 13 domains that are important across SMI diagnoses (e.g., depression, anxiety, psychosis, mania, sleep problems, self-harm, substance use, etc.) with higher scores indicating more severe total symptoms. The CCSM has been found to have strong validity and reliability in SMI samples.

Health-related quality of life will be examined using the SF-12 comprised of the Physical Component Summary (PCS) and Mental Component Summary (MCS). The PCS and MCS are standardized with a mean of 50 and a standard deviation of 10, with higher scores indicating better health-related quality of life. The subscales have good reliability and are predictive of health outcomes in Veterans with chronic illness.

Suicidality will be assessed with the 21-item Scale for Suicidal Ideation (SSI), an interviewer rated measure of a continuum of suicidal ideation, including thoughts, attitudes, plans, and behaviors. SSI items are scored on a 0 to 2 Likert scale, with higher scores indicating greater intensity of suicidal ideation. The SSI has strong psychometric properties in outpatients with psychiatric conditions.

Collected from a CAPRI/CPRS/JLV data pull, service utilization data will include days of psychiatric hospitalizations. Lead by [name], this service utilization data will be extracted from the Corporate Data Warehouse.

#### *Other measures and covariates*

Sociodemographic and background questionnaire (Appendix 10): Used broadly in previous work studies, a standard background and demographic questionnaire will probe gender, age, ethnicity, education, medical conditions, substance use, military history, residential status, disability entitlements, and legal history. Given its association with future work outcomes found in past studies, work history will be assessed via self-report, CAPRI/VCPRS/JLV chart review, and SE staff report for verification; these variables will include longest past competitive job, weeks worked and wages earned in the 6 and 9 months preceding baseline. Collected via CAPRI/CPRS/JLV chart review, time spent in SE services, operationally defined as the number of days receiving SE services, will be examined as a possible covariate. Session attendance for CBTw and psychoeducation will also be tracked.

### **Staff Participation: CBTw Implementation (Aim 3)**

In order to ensure successful implementation of CBTw during WORKWELL and wide-scale uptake following its completion, an evaluation of this initial implementation strategy and barriers and facilitators of implementation will be conducted, guided by the RE-AIM framework.

#### *Implementation Activities*

Training (Months 1-3): [name], [name], and the project manager will conduct onsite or virtual trainings. VRCs delivering CBTw will attend a half-day CBTw workshop consisting of: 1) Education on CBTw content and application of cognitive, behavioral, and narrative strategies; 2) Mock practice of facilitation strategies; 3) Customization of CBTw content to meet unique needs of Veterans. Second, led by [name], psychoeducation facilitator training will follow a parallel structure. Third, other SE staff will be oriented to study procedures. Fourth, SE managers overseeing VRCs will receive training on how to provide supervision to ensure CBTw implementation.

Fidelity monitoring & feedback (~Monthly): Lead by [name], adherence to the CBT model will be assessed by the Cognitive Therapy Scale-Revised (CTS-R). All CBTw and psychoeducation sessions will be audio-recorded to rate fidelity. At each site, 3 sessions from each group cohort (i.e. 1 session out of every 4) will be randomly selected for rating (in the CBTw and psychoeducation arms). On a monthly basis, consultation lead by [name] and [name], via tele or video, will include review of fidelity scores and recommendations to improve as needed. Psychoeducation facilitators will also be given fidelity feedback if they begin to drift toward CBT elements.

CBTw consultation (weekly) will be led by [name] and the project manager via tele or video with VRC CBTw facilitators and SE program managers. Consultation will feature the CBTw Facilitator Guide (Appendix 3) that was piloted in earlier work. In addition, strength based consultation will focus on Veteran case conceptualization, with an emphasis on understanding participants' recovery paths, applying CBTw strategies to fit goals and employment trajectories as they evolve over time, and problem solving obstacles.

#### *Implementation Interviews & Site visits:*

RE-AIM domains of implementation, adoption, and maintenance will be examined through semi-structured key stakeholders' interviews, lasting approximately 1 hour each. The interviews will also focus on understanding reasons to uptake and continue CBTw and important issues related to inner context and outer context (See Appendix 6). Interviews will also centrally focus on identifying barriers and facilitators to CBTw implementation within SE programs.

Interviews will be conducted in-person during periodic site-visits, or via phone/video, by Drs [name] & [name]. Site visits will take place at pre-implementation (1 month), early implementation (~Month 6), mid-implementation (first quarter-Year 2), and later implementation (first quarter-Year 3) will be conducted. During day-long visits, Drs. [name] and [name] will interview VRCs delivering CBTw, SE staff and managers, and make observations of CBTw processes. The implementation support team will keep detailed field notes recording activities conducted, barriers and facilitators encountered, and strategies utilized to address these. Site visitors will produce a written report that will provide a narrative summary of implementation strengths and weaknesses.

## **5.6 Data Analysis**

### **Sample size and power**

**276 total participants** (138 per study arm) will be needed to ensure > 80% power for this two-arm trial, accounting for the clustering effect of CBTw group cohort and potential attrition of 13%.

### **Analyses:**

Study analyses will be conducted by study personnel associated with the Richard L. Roudebush VAMC, as noted in section 4.0, Resources and Personnel.

### *Preliminary Analyses:*

Given the RCT design, characteristics of participants are expected to be balanced across the two study arms. Baseline characteristics and baseline clinical outcomes (e.g., symptoms) will be compared between the arms using the appropriate test (i.e., t-test, or Chi-square test). Variables found to significantly differ will be included as covariates in the primary

analyses. All primary analyses will also include time receiving SE services and site membership as covariates. The potential interaction effects of site with key predictors will also be included as predictors to account for the site effect. Lastly, attendance (the number of CBTw or psychoeducation sessions attended) and the association with the Aim 1 and Aim 2 outcomes will be examined.

#### *Competitive Work Outcomes (Hypothesis 1)*

For the outcome, total weeks worked in competitive jobs, three-level linear regression models will be used to test the effects of CBTw + SE compared to psychoeducation + SE over time, with predictors of study arm, arm by time interaction, site, and interaction between site and key predictors, covariates, as well as random effects to accommodate the potential non-independence due to repeated measures and group cohort effects. The time effects could be linear or nonlinear; these possibilities will be examined by treating time as continuous or categorical. If the outcomes are not normally distributed, robust maximum likelihood estimation method will be used to correct the standard error estimates for nonnormality. In the case of excess of zeros for this outcome, hurdle negative binomial models, a reliable method to analyze zero inflated longitudinal data of this nature, will be utilized. For the binary outcome, steady competitive work status across the 12-month study period, two-level logistic regression model will be used with the same set of predictors as in the linear models, with random effects to accommodate the potential non-independence due to group cohort effects.

#### *Health and Recovery Outcomes (Hypotheses 2a & 2b)*

To test **Hypothesis 2a**, three-level linear regression models (i.e. mixed models) accounting for the nested nature of the data will be used to test the effects of CBTw + SE services compared to psychoeducation + SE on each of the continuous outcomes including recovery (RAS), health-related quality of life (PCS & MCS), symptoms (CCSM), and suicidality (SSI) over time. For the count outcome of service utilization, three level Poisson regressions will be used to examine group differences over time on number of days of inpatient hospitalization. If there is a problem of excess of zeros for utilization (e.g., no hospitalizations), hurdle negative binomial models will be used.

To test **Hypothesis 2b**, three-level linear regression models will examine the effects of work on health and recovery outcomes over time, with predictors of competitive weeks worked, time, weeks by time interaction, site membership and potential interaction between site and key predictors, potential covariates (i.e. controlling for baseline levels of health and recovery), as well as random effects to accommodate the potential non-independence due to repeated measures and group cohort effects.

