## **5.3 Recruitment Methods**

### **5.3.1 Number of Subject**

#### **Needed Veterans**

276 total participants (138 per study arm) will be needed to ensure > 80% power for this two-arm trial, accounting for the clustering effect of CBTw group cohort and potential attrition of 13%. The study sample will include around 50% minority participants, and 5% Hispanic; these figures are consistent with CBTw pilot studies which included 48% African American participants. These are also representative of the mean number of non-white Veterans served at RLR, Hines, and St. Louis. In FY18, 48.7% of Veterans at these facilities were non-white, 46.2% Caucasian, and 2.7% identified as Hispanic or Latino. In the CBTw pilot studies, 10% women Veterans were recruited, consistent with gender distribution of Veterans served by the 3 study facilities (mean of 10.8% of Veterans identify as female in FY18). In WORKWELL, comparable numbers of women Veterans will be recruited. Data analyses will examine differences in outcomes based on gender and ethnicity, although these analyses may be underpowered to

detect significant differences.

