## 5.6 Study Evaluations

### Data Collection Protocol for Study Aims 1 & 2

Conducted by onsite research assistants (RAs) blinded to arm assignment, outcomes assessments will take place at four time points: baseline, 12-weeks (posttreatment), 6 months, and 9 months. In addition, work outcomes will be collected monthly on Work Update Forms to lessen the burden of Veteran recall. This schedule will elucidate the trajectory of treatment effects over time, including early response and more sustained impacts on outcomes. Participants will receive \$20 for each completed outcome assessment (baseline, 12-week, 6 & 9 month only). After obtaining informed consent, the onsite RA will administer a baseline assessment to gather assessment data. Each assessment will take approximately 60 minutes. All baseline assessments will take place in person; 12 week, 6 month, and 9 month assessments may be done in person (first consideration) or by phone.

The primary work outcome, total weeks worked in competitive jobs, will be collected monthly and analyzed at all assessment points with the primary endpoint being 6 months to allow adequate time for CBT skills to be practiced and solidified. The 12 month endpoint will examine whether there are sustained effects of CBTw and determine whether there are differences between the arms on achievement of steady competitive work (Aim 1). Health and recovery outcomes will be examined between the arms at all assessment points to understand the impact of CBTw; the relationship between weeks worked and these outcomes will also be examined at all assessment points (Aim 2). Work outcomes may be collected in person or by phone.

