Statistical Analysis Plan

Protocol Number: CIRB 20-08

Work as a determinant of health: A pragmatic trial of enhanced cognitive behavioral therapy to competitive work and wellness in veterans with serious mental illness (WORKWELL)

Funding Agency: HSR&D

9/30/2025

Analysis Plan

Statistical Considerations

Sample size and power

276 total participants will be needed to ensure > 80% power for this two-arm trial, accounting for the clustering effect of CBTw group cohort and potential attrition of 13%.

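### Inpatient days default to a Poisson model with an undefined excess-zeros exit, no overdispersion provision, no named deciding test in the hurdle fallback, and no analysis in the SAP

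*Protocol*

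**What the plan says.** Protocol section 3.2 lists inpatient service utilization among the Hypothesis 2a outcomes. The Aim 2 measures section specifies the data: "service utilization data will include days of psychiatric hospitalizations". The protocol's data analysis section, under Health and Recovery Outcomes, sets the default: "three level Poisson regressions will be used to examine group differences over time on number of days of inpatient hospitalization". It gives one exception: "If there is a problem of excess of zeros for utilization (e.g., no hospitalizations), hurdle negative binomial models will be used".

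Four things are not stated for this outcome: what counts as an excess of zeros, the random-effects structure of the Poisson model, whether time is linear or categorical, and the window over which days are counted at each assessment. The robust-estimation clause ("robust maximum likelihood estimation method will be used to correct the standard error estimates for nonnormality") is written for weeks worked in the Hypothesis 1 section and is not extended to the Poisson model.

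Under Hypothesis 2a the SAP lists only the continuous outcomes (RAS, PCS and MCS, symptoms, SSI). It contains no model for inpatient days and does not say that the outcome was withdrawn.

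**The concern.** A Poisson model treats each hospital day as a separate event. In fact one admission puts a block of days into one person's count for one period. A person random intercept absorbs lasting differences between people, but not this bunching within a period, and the arm-by-time test is judged against within-person variation. Its standard error is then too small.

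The written exit responds to zeros, not to variance. It has no test or threshold, so the model would be chosen after the data are seen. The fallback also splits the question in two (any admission, and days given admission) without saying which answer decides. Fewer inpatient days would be a service-system claim, so a false positive here would matter beyond the trial.

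**Working it through.** The documents give no power, rate, variance or error figure for inpatient days, so there is nothing to reproduce.

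**Inputs from the documents.** There are 276 participants, 138 per arm, and 13% attrition: 276 x 0.87 = 240 analysed, 120 per arm. Assessments are at baseline, 12 weeks, 6 months and 9 months.

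**Assumptions.** Admission rate and length of stay; two-sided alpha of .05 (the SAP states .05 for Aim 1 only); person random intercepts; model-based standard errors. Cohort intercepts are left out because they do not affect a within-person time contrast.

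**Step 1: overdispersion.** If stays arrive at random and have length L, within-person overdispersion is phi = E(L^2)/E(L). For constant stays phi = L. For geometric stays with mean m, phi = 2m - 1.

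**Step 2: type I error of the Poisson arm-by-time test.** Linear time (1 df): 2[1 - Phi(1.96/sqrt(phi))]. Three categorical periods (2 df): exp(-2.996/phi).

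| Assumed stay | phi | Linear time | Three periods |
|---|---|---|---|
| 1 day | 1 | 5% | 5% |
| constant 3 days | 3 | 26% | 37% |
| constant 5 days | 5 | 38% | 55% |
| constant 8 days | 8 | 49% | 69% |
| geometric, mean 5 | 9 | 51% | 72% |
| geometric, mean 8 | 15 | 61% | 82% |

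For linear time to exceed 50%, phi must exceed (1.96/0.674)^2 = 8.4. That is a mean stay of 8.4 days if constant, or (8.4 + 1)/2 = 4.7 days if geometric.

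**Step 3: simulation with no treatment effect.**
- Linear time, four quarterly counts, 5% admitted per quarter, conditional Poisson, 3,000 trials per setting. Constant stays: 5.7% (1 day), 26.5% (3), 37.7% (5), 45.6% (7). Geometric stays: 35.8% (mean 3), 53.0% (5), 60.5% (7), 71.7% (14).
- A fitted random-intercept Poisson model, 300 trials per setting, gives 55-65% at a geometric mean of 7 days with 2-20% admitted per quarter. Length of stay drives the result far more than the admission rate does.
- Three periods, 0.03 or 0.06 admissions per person-period, mean stays of 5 or 8 days: 39-64% with linear time, 58-83% with categorical time.
- Adding a person-level random time slope: 0-4% in nine settings, 100 trials each.

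**Step 4: would the exit be taken?** With 5% admitted per quarter and a geometric mean of 7 days, 95% of counts are zero, against 84.5% predicted by the fitted random-intercept Poisson. A parametric bootstrap found excess zeros in 40 of 40 trials. It did so in 40 of 40 trials in each of three other settings, which included mean stays of 2 and 3 days.

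**Step 5: the hurdle fallback under no effect.** Geometric mean 7 days, 400 trials per row; the truncated part was fitted without random effects.

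| Admitted per quarter | Zero part | Days part | Joint 2-df test | Either part at .05 |
|---|---|---|---|---|
| 2% | 4.8% | 10.0% | 7.5% | 14.0% |
| 5% | 5.8% | 6.8% | 5.0% | 12.2% |
| 10% | 5.5% | 5.5% | 6.5% | 10.2% |

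**Step 6: sparsity.** At 0.03 admissions per person-period, 240 x 3 = 720 person-periods give 720 x (1 - exp(-0.03)) = about 21 non-zero counts, to be shared between two arms and three periods.

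**The case against.** The best defence is that the plan would probably not use the Poisson model. An outcome that is zero for most people in most periods is what the exit clause describes. Step 4 supports this: the zeros were in excess even of what a random-intercept Poisson predicts. The fallback is a negative binomial model, so it carries a dispersion parameter, and its joint test runs at 5.0-7.5%. The term three-level also does not rule out a random time slope, which would remove the inflation. All of this stands.

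It follows that three stronger readings are not supported. A reader might infer that the planned test would be falsely significant in more than half of null trials. That needs an assumed length of stay, intercepts only, model-based standard errors and a retained Poisson model, and with linear time it fails even for constant stays of 5 or 8 days. A reader might infer that random intercepts could fit the zeros so well that the exit is never triggered; the check points the other way. And a reader might say that the plan's intervals for this outcome are too narrow, but neither document states any.

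The defence does not supply a criterion for the switch, a random-effects structure, a deciding test within the hurdle model, or an analysis in the SAP. Nor does it help if only about 21 non-zero counts must support an arm-by-time estimate.

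**Conclusion.** The point holds as a gap in specification with a potentially large effect on error, for one secondary outcome. It does not touch the primary analysis of weeks worked. The size depends on the route taken:

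- Random-intercept Poisson kept, with model-based standard errors: about 25-65% (linear time) or 37-83% (three categorical periods), for assumed mean stays of 3-8 days. With one-day stays there is no material inflation.
- Person-level random slope included: no inflation.
- Hurdle fallback used, the more likely route: near nominal on a joint test, about 10-14% if either part counts as a finding.

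The plan does not say which of these applies, and the SAP is silent on the outcome altogether.

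**What to change.** In the protocol's Health and Recovery Outcomes analysis, and in a new paragraph under SAP Hypothesis 2a, replace the Poisson default and the data-dependent switch with one pre-specified overdispersion-robust analysis of total inpatient days per participant over follow-up. Two workable options:

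- A negative binomial model with arm, site and an offset for log follow-up time, and cohort-robust standard errors with a small-sample correction. The correction is needed: without it, null rejection ran slightly high, at 6-9%, at the assumed rates.
- A permutation test within site that respects the group cohorts. Permuting person totals held 3-6% in null runs at the same assumed rates.

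Name one deciding test, define the counting window, and report any admission (yes or no) alongside. If the sponsor prefers the hurdle model, make it the sole model, state its random effects, and name the joint test or one part as decisive.

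The cost is wording in two documents. The downside is a wider interval, and the per-period arm-by-time contrast, which Aim 2 envisages at 12 weeks, 6 and 9 months, becomes descriptive for this outcome.

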#### *Missing data: Aims 1 & 2*

Missing data from Aims 1 and 2 will come in two different forms: missing by attrition and intermittent missing of observation. Using logistic regression, the effects of missing observations due to sample attrition will be examined by investigating the participant characteristics associated with dropout. If results reveal that data are missing completely at random (MCAR) or due to observed factors (MAR), the data will be analyzed using full information maximum likelihood, taking into account potential predictors for missingness. However, if the pattern of missing data is nonignorable; pattern-mixture models that includes variables defined by the participant's pattern of missing data will be used. Sensitivity analyses also will be performed to examine how the result will change based on different assumptions about the missing data, such as the missing work period having no work, the mean amount of work as available data from earlier follow-up periods, or full employment.

